15.1.3.1. Calculation of difference in proportion (STEP 2 details)

The Week 16 endpoint will be analyzed using (M1) model.

The following SAS code will be used:

```
proc genmod data=data_PASI75_week_16 descend;
  class PASI75(ref="N") TRTP(ref="HUMIRA") EXPOS_BIO(ref="N") /
  param=GLM;
  model PASI75=TRTP BASELINE_PASI EXPOS_BIO/ dist=binomial link=logit;
  lsmeans TRT / ilink OBSMARGINS diff=all;
run;
```

The population adjusted natural scaled proportion at Week 16 are the estimates produced by the LSMEANS statement.

Document: \\eedc-nas01a:\Boehringer_Ingelheim\BI_695501\XXA39605\Biostatistics\Documentation\SAP\15-v2.0\BI 1297.12 SAP v2.0 31JAN2018.docx

Author: Version Number: 2.0
Version Date: 31JAN2018

Template No: CS_TP_BS016 Revision 4
Effective Date: 01Apr2016

Reference: CS_WI_BS005

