7.7 DETERMINATION OF SAMPLE SIZE

To perform the equivalence test BI 695501 versus US-licensed Humira with $\geq 85\%$ power, approximately 300 patients are needed for this comparison (FAS).

For the calculation of the sample size a meta-analysis on Week 16 data of the REVEAL and CHAMPION trials ([R14-4849](#), [R14-4898](#)) was performed. This meta-analysis revealed a risk difference of 64.2% and a 95% CI (60.4% to 67.9%). [Table 7.7: 1](#) shows the information used in the meta-analysis.

The classical 95-50-95 approach would give a non-conservative acceptance margin of 30.2% for the risk difference preserving 50% of the Humira effect.

Calculation of a conservative equivalence margin

Preserve 70% of the lower confidence limit (lcl) 60.4% (obtained from the meta-analysis) of the historical effect over placebo. Equivalence margin = $(1 - \text{preserved proportion}) * \text{lcl}$, $(1-0.7)*60.4\% = 18\%$.

Table 7.7: 1 CHAMPION and REVEAL results

Humira versus Placebo	Treatment			Placebo		
	Events	Total	%	Events	Total	%
CHAMPION	86	108	79.6%	10	53	18.9%
REVEAL	578	814	71%	26	398	7%

The weighted mean response rate is assumed to be the true response rate of 72%. This sample size is based on an assumed treatment difference in proportions of patients with PASI 75 at Week 16 of 0%, a standard proportion of 72% and an equivalence margin of 18%. At a power of 85% the sample size would be 288.

[Table 7.7: 2](#) presents the sample size at different margins and different power.

Table 7.7: 2 Sample size according to different scenarios

Assumed true response rate (RR)	Margin	Confidence level (two-sided)	Power	Sample Size [#] Equivalence
72%	15%	95%	75%	340
72%	15%	95%	80%	366
72%	15%	95%	85%	414
72%	15%	95%	90%	572
72%	18%	95%	75%	234
72%	18%	95%	80%	256
72%	18%	95%	85%	288
72%	18%	95%	90%	330
72%	20%	95%	75%	188
72%	20%	95%	80%	200
72%	20%	95%	85%	228
72%	20%	95%	90%	262

[#] Allocation ratio 1:1

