6.5. STATISTICAL TESTS

The default significance level will be (5%); confidence intervals will be 95% and all tests will be two-sided, unless otherwise specified in the description of the analyses.

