15.1.3. PRIMARY ANALYSIS OF PRIMARY EFFICACY VARIABLE

The primary efficacy analysis will be performed for the FAS.

The primary objective of this trial is to test the hypothesis that BI 695501 and US-sourced Humira are equivalent.

The test for equivalence will be performed with respect to BI 695501 versus US-sourced Humira.

The hypotheses for the equivalence test can be written as follows:

- H_0 : Difference in PASI 75 response rates at Week 16 (BI 695501 minus US-sourced Humira) is less than -18.0% or more than 18.0%
- H_1 : Difference in PASI 75 response rates at Week 16 (BI 695501 minus US-sourced Humira) is within [-18.0%, 18.0%]

To conclude equivalence, the two-sided 95% CI of the difference in PASI 75 response rate (BI 695501 – Humira) rounded to 1 decimal place has to be fully within the equivalence limits of $\pm 18.0\%$.

The primary analysis of the difference in PASI 75 response rates at Week 16 will be based on logistic regression with subsequent transformation of the estimated parameters to the difference in proportions.

The estimates from the logistic regression are on the logit scale, and the difference in proportions will be calculated as the difference between the predicted probabilities in the treatment groups on the original scale, with the variance calculated using the cumulative distribution function method of Reeve (Reeve 2016).

The statistical model can be described as follows:

(M1) $\text{Logit}(\text{response to treatment at Week 16}) = \text{Treatment} + \text{Baseline PASI} + \text{Prior exposure to a biologic agent} + \text{random error}$

This model includes fixed, categorical effects of:

- Treatment (BI 695501 versus US-sourced Humira)

Document: \\ieedc-nas01a:\Boehringer_Ingelheim\BI_695501\XXA39605\Biostatistics\Documentation\SAP\15-v2.0\BI 1297.12 SAP v2.0 31JAN2018.docx

Author:

Version Number:

2.0

Version Date:

31JAN2018

Template No: CS_TP_BS016 Revision 4
Effective Date: 01Apr2016

Reference: CS_WI_BS005

- Prior exposure to a biologic agent (Yes versus No)

and continuous effect of:

- Baseline PASI

The random error is assumed to be binomially distributed.

The analysis will consist of the following four steps:

STEP 1: Starting from the incomplete dataset, data imputation method are applied (described in section 15.1.2) to generate 1000 completed datasets.

STEP 2: Calculation of difference in proportion based on adjusted PASI 75 responders

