APPENDIX 6. SAS CODE FOR DIFFERENCE IN PROPORTION CIs

```
%let K=1000000; /*number of simulation*/
%let alpha=0.05; /*confidence level*/

proc IML;
  /*create theta and vartheta*/
  theta={&G. &Z.}; print theta; /*create theta vector*/
  vartheta={&VARG. &COVGZ. , &COVGZ. &VARZ.}; print vartheta; /*create
vartheta vector*/

  /*Create Xc the cholesky decomposition of Vartheta*/
  Xc = t(root(Vartheta));

  /*create X random normal vector*/
  call randseed(456); /* set random number seed */
  X = j(&K.,2); /* allocate the X vector */
  call randgen(X,"Normal");

  /*Write X matrix in a sas dataset called X*/
  X1=X[,1];
  X2=X[,2];
  create X var{X1 X2};
  append;
  close X;

  /*Calculate Y = X %% Xc*/
  Y=X*Xc;

  /*G,Z*/
  G=Y[,1]+Theta[1,1];
  Z=Y[,2]+Theta[1,2];
  DELTA=(1/(1+exp(-(G+Z))))-(1/(1+exp(-Z)));
  call sort(DELTA);

  LOW=DELTA[round(&k.*(&alpha./2))]; print low;
  UP=DELTA[&K.-round(&k.*(&alpha./2))]; print up;

quit;
```

Document: \\needc-nas01a:\Boehringer_Ingelheim\BI_695501\XXA39605\Biostatistics\Documentation\SAP\15
-v2.0\BI 1297.12 SAP v2.0 31JAN2018.docx

Author: Version Number: 2.0
Version Date: 31JAN2018

Template No: CS_TP_BS016 Revision 4
Effective Date: 01Apr2016

Reference: CS_WI_BS005

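### The primary risk difference is computed at one average-covariate profile, not averaged over patients as the hypotheses, the label and the ±18% margin imply

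*SAP*

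**What the plan says.** The target is a difference between group response rates. SAP 15.1.3 states the alternative hypothesis as "Difference in PASI 75 response rates at Week 16 (BI 695501 minus US-sourced Humira) is within [-18.0%, 18.0" percent. Protocol 7.7 derives the margin on that same scale from arm-level event counts in two placebo-controlled trials: "This meta-analysis revealed a risk difference of 64.2% and a 95% CI (60.4% to 67.9" percent), then "Preserve 70% of the lower confidence limit (lcl) 60.4% (obtained from the meta-analysis) of the historical effect over placebo". The sample size also uses a group rate: "The weighted mean response rate is assumed to be the true response rate of 72" percent.

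The computation is in three places.

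- SAP 15.1.3.1 fits model M1 (treatment, baseline PASI, prior biologic exposure, logit link) and requests least-squares means with the ILINK and OBSMARGINS options. It describes the output thus: "The population adjusted natural scaled proportion at Week 16 are the estimates produced by the LSMEANS statement".
- SAP 15.1.3.2 builds the interval from g, the treatment coefficient, and z, the linear predictor at one covariate vector x*. The SAP does not define x*.
- SAP Appendix 6 evaluates, in each draw, "DELTA=(1/(1+exp(-(G+Z))))-(1/(1+exp(-Z" (closing brackets omitted): one G and one Z, with no sum over patients.

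**The concern.** Least-squares means are formed on the logit scale. Baseline PASI is set to its mean, and OBSMARGINS weights the prior-biologic classes by their observed shares, still on the logit scale. ILINK then applies the inverse logit once. Because the inverse logit is curved, the probability at the average covariates is not the average of the patients' probabilities. No step averages predicted probabilities over the FAS, so the code does not deliver a population-averaged response rate.

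Two things are at stake in the single confirmatory test. First, the interval is compared with ±18 points on a scale for which that margin was not derived. Second, covariate adjustment in a logistic model can shorten the interval for the population-averaged difference, and evaluation at one profile gives up nearly all of that gain.

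**Working it through.** **Inputs from the documents.** Humira response rate 72% (Protocol 7.7: (86+578)/(108+814) = 664/922 = 72.0%). Margin (1 − 0.7) × 60.4 = 18.1, stated as 18 points. True difference 0, 1:1 allocation, 288 patients for 85% power, about 300 planned. Two-sided 95% intervals (SAP 6.5).

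**Assumptions.** The documents give no prognostic strength for baseline PASI or prior biologic. I take the covariate part of the linear predictor as normal with SD s = 0.3, 0.5 or 0.8 on the log-odds, and read x* as the average profile that the least-squares means use.

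**1. Reproduce the plan's figure.** n per arm = 2 × 0.72 × 0.28 × (1.960 + 1.440)² / 0.18² = 143.8, so 144 per arm and 288 in total. This matches Protocol 7.7. At N = 300 the SE is √(4 × 0.2016/300) = 5.18 points, and power is 2Φ(0.18/SE − 1.96) − 1 = 86.9%. This calculation takes no credit for covariates.

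**2. Difference at the average profile.** For each arm, find the intercept a at which the mean of expit(a + s·X), X standard normal, equals the arm's true rate (72% for Humira; 54% or 90% for BI 695501). The rate at the average profile is expit(a).

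| s | Humira (true 72%) | BI (true 54%) | difference (true −18) | BI (true 90%) | difference (true +18) |
|---|---|---|---|---|---|
| 0.3 | 72.4 | 54.1 | −18.3 | 90.3 | +17.9 |
| 0.5 | 73.1 | 54.2 | −18.8 | 90.9 | +17.8 |
| 0.8 | 74.5 | 54.6 | −19.9 | 92.0 | +17.5 |

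At a true −10 the values are −10.1, −10.4 and −10.9. At 0 the difference is 0 for every s.

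**3. Precision at a true difference of 0, N = 300.** Let w be p(1 − p) for a patient and p* the rate at the average profile. The treatment coefficient has variance 4/(N·E[w]). The difference at the average profile then has variance 4[p*(1 − p*)]²/(N·E[w]). The difference averaged over all patients (standardised) has variance 4E[w]/N. The crude difference has 4 × 0.2016/N.

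| s | E[w] | [p*(1−p*)]²/E[w] | power, average profile | power, standardised |
|---|---|---|---|---|
| 0.3 | 0.198 | 0.202 | 86.9% | 87.7% |
| 0.5 | 0.192 | 0.202 | 86.9% | 88.9% |
| 0.8 | 0.180 | 0.201 | 87.1% | 91.4% |

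The average-profile variance stays at the crude 0.2016 within rounding, while the standardised variance falls to 0.98, 0.95 and 0.89 of it.

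**4. Error rates by simulation.** These used 6,000 trials of 300 patients per setting, s = 0.5, an assumed 20% prior biologic use and delta-method intervals. At a true +18 equivalence is concluded in 2.9% of trials at the average profile and 2.2% standardised. At −18 the figures are 1.5% and 2.2%. The nominal rate is 2.5%, with Monte Carlo error about √(0.025 × 0.975/6000) = 0.2 points.

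**The case against.** **It is a choice of estimand.** Protocol 7.3.1 prespecified a difference in model-predicted probabilities with the Reeve method, and the SAP's population label may mean only that OBSMARGINS uses observed margins. The first part stands: the average-profile difference is a legitimate quantity. But the hypotheses and the margin are stated for response rates, the SAP does not acknowledge the distinction, and weighting on the logit scale does not make the result a population average.

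**The size rests on assumption.** This stands. Entry requires PASI of at least 12 and at most one prior biologic, and the endpoint is already relative to baseline, so the covariates may be weak. At s = 0.3 the shift is 0.1 point at +18 and 0.3 at −18, and the forgone power is under one percentage point.

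**The power figures do not describe the full pipeline.** They use delta-method or asymptotic variances, without Appendix 6 draws, back-calculated standard errors or multiple imputation. They compare two estimators on equal footing and should not be read as the power of the code as written. Appendix 6 also multiplies its normal draws by a transposed Cholesky factor, which does not reproduce the intended covariance. That is a separate matter and is not counted here.

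**Stronger readings a reader might infer.** One is that the average-profile difference is always larger in absolute size, so the test is merely conservative. The table shows the reverse at +18. Another is that the trial is underpowered because of this choice. It is not: 288 takes no covariate credit, and power at 300 stays near 87%. A third is a gross loss of error control. In the same simulation the rate at +18 reaches 6.1% or 14.5%, but only for s = 1.0 or 1.5, and nothing in the documents supports covariates that strong.

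**Conclusion.** The concern holds in this form: the primary analysis estimates a difference at one average-covariate profile, while its hypotheses, label and margin refer to the difference in response rates over the trial population. At a true difference of 0, the planning assumption, there is no discrepancy. At the margins, for s up to 0.8, the lower side is conservative by 0.3 to 1.9 points and the upper side anti-conservative by 0.1 to 0.5 points. Planned power is intact; what is forgone is about 1, 2 or 4 percentage points of available power. All of these sizes depend on a covariate strength that the documents do not give, and they are small if it is weak. The change is worth making because this is the only confirmatory test and the mismatch can be removed within the existing model.

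**What to change.** In SAP 15.1.3.1, replace the least-squares-means step. In each imputed dataset, after fitting M1:

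1. Predict the response probability of every FAS patient with treatment set to BI 695501, and again with treatment set to Humira.
2. Average each set over all FAS patients, regardless of the arm they were randomised to, and take the difference.
3. Obtain the interval by the delta method, or by drawing from the full coefficient covariance matrix and averaging DELTA over all patients in each draw. Change SAP 15.1.3.2 and Appendix 6 to match.
4. Pool by Rubin's rules as in STEP 4.

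The text must say that the average runs over all patients. If each arm's own patients are averaged under their own treatment, the score equations of M1 return the observed arm rates. The result is then the crude difference, with no gain in precision.

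The model, the imputations and the pooling are unchanged. The cost is a SAP and code change before unblinding and somewhat more computing, which the delta method or fewer draws would limit.

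If the sponsor prefers the average-profile difference, the SAP should define x*, drop the population label, restate the hypotheses for that quantity and justify ±18% for it.

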15.1.3.2. Calculation of confidence interval (STEP 3 details)

The difference in proportion at Week 16 is produced in STEP 1.

The Week 16 confidence interval for the estimated difference in proportion are produced using the cumulative distribution function method of Reeve (Reeve 2016).

The SAS code to implement the method is provided in APPENDIX 6 and required as input:

1. Variance (g) is directly provided by SAS PROC GENMOD Empirical Standard Error Estimates.
2. $Cov(b_i, b_j)$ and $Cov(\gamma, b_i) \forall i, j \in [0; k]$ are directly provided by SAS PROC GENMOD Covariance Matrix (Empirical).
3. Variance (z) will be calculated using the formula:

$$Var(z) = Var\left(b_0 + b_1x_1^* + \dots + b_kx_k^*\right) = \sum_{i,j=0}^k x_i^* x_j^* Cov(b_i, b_j) \text{ where } x_0^* = 1$$

4. Covariance (g,z) will be calculated using the formula:

$$Cov(g, z) = Cov\left(\gamma, b_0 + b_1x_1^* + \dots + b_kx_k^*\right) = \sum_{i=0}^k x_i^* Cov(\gamma, b_i)$$

Then VarTheta is equal to $\begin{pmatrix} Var(g) & Cov(g, z) \\ Cov(g, z) & Var(z) \end{pmatrix}$

15.1.3.3. Computation of the final confidence interval with missing data method (NRI+MI) (STEP 4 details)

STEPS 1 and 2 are repeated on each imputed dataset produced by the multiple imputation method (fixed to 1000 datasets).

Estimated risk difference ($RD_{estimated}$) per imputed datasets is calculated using STEP 1.

Using Lower and Upper bounds calculated with Reeve's method per imputed datasets in STEP 2, and assuming that risk difference is normally distributed, the estimated standard error ($SE_{estimated}$) is calculated as:

$$SE_{low} = (RD_{estimated} - \text{Lower Bound}) / (z_{\alpha/2})$$

$$SE_{up} = (\text{Upper bound} - RD_{estimated}) / (z_{\alpha/2})$$

Where $z_{\alpha/2} = 1.96$ for 95% CI bounds

$$SE_{estimated} = \text{mean}(SE_{up}, SE_{low}).$$

The couple ($RD_{estimated}, SE_{estimated}$) per imputed dataset is then combine using Rubin's Rules to produce the final confidence interval.

The following SAS code will be used to combine the results:

Document: \\eedc-nas01a:\Boehringer_Ingelheim\BI_695501\XXA39605\Biostatistics\Documentation\SAP\15-v2.0\BI 1297.12 SAP v2.0 31JAN2018.docx

Author: Version Number: 2.0
Version Date: 31JAN2018

Template No: CS_TP_BS016 Revision 4
Effective Date: 01Apr2016

Reference: CS_WI_BS005

```
proc mianalyze data=data_RD_SE_per_MI_dataset;  
  modeleffects RD_ESTIMATE;  
  stderr RD_SE;  
run;
```

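### SAP 15.1.3.2 names a standard-error table as the source of Var(g); entered unsquared, it widens the primary CI beyond the ±18-point margin at the planning values, and the Appendix 6 code needs its own correction

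*SAP*

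**What the plan says.** SAP 15.1.3 sets the decision rule, which opens: "To conclude equivalence, the two-sided 95% CI of the difference in PASI 75 response rate". The difference is taken as test product minus reference. The section then requires that this interval, "rounded to 1 decimal place has to be fully within the equivalence limits of" the margin, which is 18.0 points either way. The limits come from simulation on the logit scale, where g is the treatment coefficient and z the linear predictor of the reference arm.

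SAP 15.1.3.2 lists the inputs to that simulation. Item 1: "Variance (g) is directly provided by SAS PROC GENMOD Empirical Standard Error Estimates". Item 2 takes the covariances among the other coefficients, and between them and the treatment coefficient, from GENMOD's empirical covariance matrix. Items 3 and 4 give formulas for Var(z) and Cov(g,z). Together these form the 2×2 matrix VarTheta.

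Appendix 6 builds the matrix as "vartheta={&VARG. &COVGZ. , &COVGZ. &VARZ" and goes straight to a Cholesky decomposition, with `Xc = t(root(Vartheta))` and `Y=X*Xc`.

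The model code in SAP 15.1.3.1 names the treatment variable TRTP in its CLASS and MODEL statements, but then has "lsmeans TRT / ilink OBSMARGINS diff=all". It contains no statement requesting empirical (sandwich) output.

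Protocol 7.7 gives the planning values. The true effect is taken as zero, and the response rate and margin are "a standard proportion of 72% and an equivalence margin of 18" points. The resulting total is stated as follows: "At a power of 85% the sample size would be 288".

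**The concern.** Item 1 says the variance comes directly from a table of standard errors. Items 3 and 4 give a formula where a calculation is needed; item 1 gives none, and Appendix 6 uses `&VARG.` without transforming it. A programmer who follows the sentence puts a standard error in one cell of a matrix whose other cells are variances and covariances. A standard error below 1 is larger than its square, so the treatment variance is overstated and the interval is too wide.

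This interval alone decides equivalence, and SAP 15.2.3.1 reuses the method for the binary secondary endpoints. If the mistake came to light only after a failed result, correcting the variance after unblinding would be hard to defend.

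The printed code does not settle what was intended, because it does not request the empirical output that items 1 and 2 rely on. Appendix 6 also has a separate fault, which remains once Var(g) is right.

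**Working it through.** **Inputs.** From protocol 7.7: 72% response in both arms, true difference 0, margin 18 points, 1:1 allocation, N = 288 calculated and about 300 planned (144 and 150 per arm). From SAP 15.1.3: two-sided 95% CI, rounded to one decimal. Assumed: no missing data, so no between-imputation variance, and no covariate effect.

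**The plan's own figure.** n per arm = 2p(1−p)(z₀.₉₇₅ + z₁₋β/₂)² / margin² = 2 × 0.72 × 0.28 × (1.960 + 1.440)² / 0.18² = 143.8, so 144 per arm and N = 288. The stated sample size reproduces.

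**Matrix elements, 150 per arm.**
- Var(z) = 1/(150 × 0.72 × 0.28) = 0.0331
- Cov(g,z) = −0.0331
- Var(g) = 2/(150 × 0.72 × 0.28) = 0.0661
- SE(g) = √0.0661 = 0.257

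**Hand check of the half-width.** With equal rates, the half-width is about 1.96 × p(1−p) × √Var(g).
- Correct Var(g): 1.96 × 0.2016 × 0.2572 = 0.102.
- SE in the variance cell: 1.96 × 0.2016 × √0.2572 = 0.200.

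**Appendix 6 simulation, then the SAP's averaging of the lower and upper SE, at zero observed difference.**

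| Per arm | Var(g) entered | Multiplication | Simulated limits (points) | Half-width (points) |
|---|---|---|---|---|
| 150 | variance | correct | −10.2, +10.2 | 10.1 (10.15 before rounding) |
| 150 | variance | as printed | −12.1, +10.5 | 11.3 |
| 150 | SE | correct | −22.5, +16.7 | 19.6 |
| 150 | SE | as printed | −23.1, +16.1 | 19.6 |
| 144 | variance | correct | −10.4, +10.4 | 10.4 |
| 144 | SE | correct | −22.7, +16.9 | 19.8 |

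The inflation at 150 per arm is 19.62/10.15 = 1.93-fold against the correct interval and 19.6/11.3 = 1.73-fold against Appendix 6 as printed.

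**By common response rate**, 150 per arm, SE entered, correct multiplication: 65% gives 21.1 points, 75% gives 18.8, 77% gives 18.1, 78% gives 17.8, 80% gives 17.1. The interval stops exceeding 18 points between 77% and 78%.

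**Probability of concluding equivalence at a true 72%/72%**, summing binomial probabilities over observed counts, 150 per arm:
- correct variance and multiplication: 0.87 (0.86 at 144 per arm), in line with the planned 85%
- correct variance, multiplication as printed: 0.81 (0.78 at 144)
- SE entered: about 0.002 (0.001 at 144)

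**Why the printed multiplication is wrong.** In SAS/IML, `root(V)` returns the upper factor U with U′U = V, so `t(root(V))` is the lower factor L with LL′ = V. Each draw is a row of X, so X×L has covariance L′L, not LL′. Here L has rows (0.257, 0) and (−0.129, 0.129). L′L has first diagonal element 0.0661 + 0.0165 = 0.0827 (from unrounded values), second diagonal element 0.0165 and off-diagonal −0.0165. The simulated Var(g) is therefore 0.0827 instead of 0.0661, and 1.96 × 0.2016 × √0.0827 = 0.114 agrees with the simulated 11.3 points.

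**The case against.** The best defence is that the SAP specifies the right quantity and mislabels only its source. Item 1 says Variance (g), the displayed matrix says Var(g), and the code says `&VARG.`. Item 2 names the covariance matrix whose diagonal holds the required element. A competent programmer would probably notice, and since the printed GENMOD code produces no empirical output, the inputs have to be resolved by someone anyway. This stands. The 19.6-point interval depends on one reading of an inconsistent sentence. The mismatch between TRT and TRTP is a naming slip with no effect on Var(g).

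It does not remove the point. The sentence giving the source of a decisive input is wrong as written, nothing elsewhere corrects it, and a pre-specified primary analysis should not rest on a silent repair.

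Three stronger readings are tempting, and the documents do not support them:
- That the trial as planned cannot conclude equivalence. This holds only if the SE goes in unsquared, and then only at zero-difference common rates up to about 77%. The documents do not show what was actually programmed.
- That equivalence might be claimed wrongly. The error only widens the interval.
- That the orientation of the Cholesky factor is immaterial. That is true of the erroneous width (19.6 points either way). With the correct variance the printed orientation moves the half-width from 10.1 to 11.3 points and makes the limits asymmetric.

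**Conclusion.** The concern holds in conditional form. Item 1 of SAP 15.1.3.2 is a specification error in the primary confidence interval. If followed literally, it removes nearly all power at the planning values, and the harm is a false failure. The named quantity and the adjacent covariance matrix make the intended value recoverable, so this is an ambiguity to close and not proof that the analysis fails.

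The Appendix 6 multiplication is smaller but needs no choice of reading: run as printed with the correct variance, it costs about 1.2 points of half-width and brings power to about 0.81 at 150 per arm, below the planned 85%.

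The figures assume no covariate effect and no imputation variance; imputation variance would widen every interval further.

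**What to change.** 1. Replace item 1 of SAP 15.1.3.2 with a statement that Var(g) is the diagonal element for the treatment parameter of the same covariance matrix that item 2 uses (equivalently, its standard error squared).
2. State whether that matrix is empirical or model-based, and add to the code in SAP 15.1.3.1 the GENMOD statement or option that outputs it.
3. Change TRT to TRTP in the LSMEANS statement.
4. In Appendix 6, compute `Y = X*root(Vartheta)`, so that the simulated pairs have covariance VarTheta. Confirm by checking that the sample covariance of Y matches VarTheta.

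Items 1 and 4 are both needed: correcting Var(g) alone leaves the half-width at about 11.3 points. The cost is a few lines of SAP text and code, with no further data or patients. The change should be dated before unblinding. If the analysis has already been run, the report should state which value and which multiplication were used.
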